Title: Assessing the Cortical Response to Noxious and Auditory Stimuli Using Near Infrared Spectroscopy in Subjects under General Anesthesia

NCT: NCT02703090

Date: May 22, 2018

Title: Assessing the Cortical Response to Noxious and Auditory Stimuli Using Near Infrared Spectroscopy in Subjects under General Anesthesia

Research Question: To determine the utility of functional near infrared spectroscopy (fNIRS) in the objective, quantitative assessment of nociception and anti-nociception (analgesia) in patients under general anesthesia. A secondary question is the use of fNIRS to measure actual or intended movement either spontaneously, in response to pain, and/or in response to auditory stimuli during general anesthesia.

Significance: This study is part of an ongoing project to determine the value of fNIRS/DOI as a tool for measurement of nociception and anti-nociception and monitoring depth of anesthesia to prevent awareness and pain in patients under general anesthesia. NIRS/DOI is capable of continuously monitoring and tomographically imaging changes in oxy- and deoxyhemoglobin concentrations as a result of noxious stimulation.

Design: Prospective cohort study.

Subjects: Pediatric and adult subjects 12-30 years of age (ASA physical status I or II) undergoing routine electrophysiology procedures in the cardiac catheterization laboratory at Boston Children's Hospital will be eligible for enrollment. We plan to study and obtain useful data sets in 45 subjects with structurally normal hearts undergoing catheter ablation of arrhythmias under planned general endotracheal anesthesia.

Parents/guardians of eligible children and adults will be approached for enrollment at the pre-catheterization evaluation

Variables: Changes in oxyhemoglobin and deoxyhemoglobin concentrations measured by NIRS. Functional NIRS, also known as diffuse optical imaging (DOI), will be used to measure (1) the hemodynamic activations in the bilateral somatosensory cortices and the prefrontal cortices in response to the noxious stimulation (pain) associated with catheter ablation of arrhythmias, and whether these activations are reduced or eliminated by remifentanil, and (2) the hemodynamic activations in the supplemental motor area to actual or intended movement either spontaneously, in response to pain, and/or in response to auditory stimuli.

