is capable of continuously monitoring and tomographically imaging changes in oxy-and deoxyhemoglobin concentrations during somatosensory stimulation, such as finger tapping, finger tactile, and electrical median nerve stimulation (Becerra, Harris et al. 2008, Minati, Jones et al. 2009, Nambu, Osu et al. 2009) and multiple applications in children (Wolf and Greisen 2009, Watanabe, Homae et al. 2010). We have also shown with fMRI studies that pain stimulation activates sensory areas. Our group has a great deal of experience performing DOI measurements simultaneously with fMRI, and have demonstrated that the functional signals measured with DOI correlate temporally with fMRI signals (Strangman, Culver et al. 2002).

In our previous work using the same approach we have shown that an acute thermal stimulus using an FDA-approved Peltier thermode produces significant and measurable effects that can be measured in a number of cortical regions in healthy volunteers (Becerra, Harris et al. 2008). We have not completed the work on simultaneous fMRI and DOT measures in healthy subjects and this continues under an approved IRB protocol at MGH, 2007-P-000270, entitled “Assessing the Cortical Response to Painful Stimuli with Diffuse Optical Imaging”.

4. Design and Methods

a. Study Design

General Procedures

We plan to study and obtain useful data sets in 45 subjects (12-30 years of age) scheduled for elective electrophysiology procedures in the cardiac catheterization laboratory and undergoing ablation of arrhythmias under planned general endotracheal anesthesia. As a number of subjects may choose to withdraw from the study following enrollment, and because some subjects will not be able to participate in the study if it is not possible to obtain adequate NIRS signals (as discussed below under Study Procedure: Day of Surgery), we plan to enroll 54 subjects to allow for drop-outs.

- **Pre-Operative Visit**

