The only substantive difference between the study protocol and standard clinical care is the administration of remifentanil. Intravenous opioids are typically not given beyond induction of general anesthesia nor during catheter ablation of the arrhythmia.

e. Definition of Primary and Secondary Outcomes/Endpoints

Primary Outcomes:

The primary outcome is the use of NIRS to measure/detect hemodynamic activations in the bilateral somatosensory cortices and the prefrontal cortices in response to the noxious stimulation

(pain) associated with catheter ablation of arrhythmias, and whether these activations are reduced or eliminated by remifentanil.

Secondary Outcome:

The secondary outcome is the use of NIRS to measure hemodynamic activation in the supplemental motor area to actual or intended movement either spontaneously, in response to pain, and/or in response to auditory stimuli.

f. Data Collection Methods, Assessments and Schedule (what assessments performed, how often)

The study will consist of enrollment and a Preoperative Questionnaire at the pre-catheterization work-up, the study protocol during two days if the patient is discharged the same day of the procedure, or three days if the subject is admitted overnight.

Prior to Preoperative Visit:

- Assessment of eligibility criteria

Pre-Operative Visit:

- Presentation of research study, informed consent/assent (20 minutes)
- Preoperative Questionnaire if patient/parents consent/assent (10 minutes)

Day of Procedure:

1) Before Procedure

- Equipment setup (20 minutes). Test run of brush and audio stimuli (10 minutes).
- BIS sensor applied to patient.

2) During Procedure

- Infusion of NaCL or remifentanil started after induction of anesthesia.
- Audio stimuli (5 seconds each) presented to the patient every half an hour.
- Electronic anesthesia record will capture relevant anesthetic and physiologic data. Study Coordinator and/or Research Nurse will document time and duration of ablations, times of catheter insertion and removal, and assure safety of the patient
- An investigator will operate the NIRS equipment.
- NIRS cap with optodes will be removed from the patient just prior to emergence from anesthesia.
- Average duration of an electrophysiologic study with catheter ablation of arrhythmias is 3 to 4 hours.

3) After Procedure

- Postoperative Questionnaire (10 minutes) will be administered before subject is discharged from the hospital, either on the day of or day following the procedure.

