d. Statistical Power and Sample Considerations

In our pilot study, we were able to collect useable data from five of the eleven subjects that were enrolled (45%). In the five subjects that produced usable results, the signal of interest had a mean value of -3.764×10^{-7} Moles with a standard deviation of 2.135×10^{-7} Moles. This results in a standardized effect size of 1.763, when using a zero mean for the null case. In order to achieve a 90% power level for this measure, the number of usable data sets is therefore eight. Considering our previous success rate of 45%, approximately 18 subjects will need to be enrolled into each group of the study for a total enrollment of 54 subjects.

e. Study Organization

The principal investigator for this study is [name], MBBCh in the Department of Anesthesiology, Perioperative and Pain Medicine at Boston Children’s Hospital. The Research Nurse(s), Study Coordinator ([name] MPH), and co-investigators ([name] MD, and [name] PhD) are members of the Department of Anesthesiology, Perioperative and Pain Medicine at Boston Children’s Hospital. Other co-investigators ([name] MD) and ([name] PhD) are members of the Department of Cardiology at Boston Children’s Hospital and Martinos Center for Biomedical Imaging, Department of Radiology, Massachusetts General Hospital), respectively. Members of the P.A.I.N. research group will participate in data collection and data analysis.

f. Data and Safety Monitoring Plan

Confidentiality will be ensured by assigning anonymous subject identification codes to each subject. The subject-screening log, which lists the names corresponding to the subject identification codes, will be kept on a locked computer, access to which is limited to only one investigator.

The risk posed to the subject in this study is minimal. Subjects will have the right to discontinue the study at any time prior to induction for any reason. Also, investigators will be in the room ready to stop the experiment in case there is any sort of adverse event. After induction of anesthesia the attending anesthesiologist and/or cardiologist may discontinue the experiment if clinical conditions warrant or in the case of an adverse event. Adverse events will be reported to the IRB as indicated above.

The investigators will review the data after the first 5 subjects and then after every 10 subjects to ensure that adequate data is being obtained.

6. Risks and Discomforts

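### The primary outcome allows a finding that remifentanil 'eliminated' activation, but the plan has no between-arm estimate or interval, and the planned arms are too small to exclude a substantial residual response

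*Combined protocol and SAP*

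**What the plan says.** The outcome definition in section 4.e concerns activation in response to noxious stimulation, "pain) associated with catheter ablation of arrhythmias, and whether these activations are reduced or eliminated by remifentanil". The Variables paragraph of the opening synopsis likewise asks "whether these activations are reduced or eliminated by remifentanil". No section attaches a threshold, margin, interval or test to the second of those two possibilities.

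Section 5.c (Data Analysis Plan) describes filtering, conversion to oxy- and deoxyhemoglobin series, a within-subject analysis, and then averaging of the optical series across subjects at matching optode positions. It names no comparison between the three arms. It does not say which hemoglobin series or which of the listed cortical regions is primary.

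Section 5.d, repeated in the synopsis under Statistical Issues, reports that in the five usable pilot subjects "the signal of interest had a mean value of -3.764×10^{-7} Moles with a standard deviation of 2.135×10^{-7} Moles". It continues: "This results in a standardized effect size of 1.763, when using a zero mean for the null case". From this it concludes: "In order to achieve a 90% power level for this measure, the number of usable data sets is therefore eight". Allowing for the 45% of pilot subjects who gave usable data, "approximately 18 subjects will need to be enrolled into each group of the study for a total enrollment of 54 subjects".

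Section 4.a and the Subjects paragraph of the synopsis set a different target for usable data: "We plan to study and obtain useful data sets in 45 subjects (12-30 years of age".

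**The concern.** Elimination is a claim that nothing, or nothing of importance, is left. It needs an estimate of what remains, with an upper limit small enough to call negligible. The plan provides neither. With no rule, an averaged trace that looks flat could be reported as elimination. The caption to Figure 2 already applies that word to a peak that disappears in one subject's trace after oral morphine.

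The scale is also open. The pilot mean is negative, both hemoglobin series are produced, and neither the primary series nor the expected sign is named. A reduction of the response is then a rise toward zero on the signed scale of the pilot signal, which the outcome does not say.

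What is at stake is the primary claim. Section 2 hopes that the work will help anesthesiologists manage analgesia and will lead to clinical trials. A report that remifentanil abolishes the cortical signal would overstate the biomarker at the point where those trials are designed.

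**Working it through.** **Inputs from section 5.d.** Pilot mean −3.764 and SD 2.135 (both ×10⁻⁷, n = 5); 8 usable sets and 18 enrolled per group; 54 in total. **From section 4.a and the synopsis:** 45 useful sets, which is 15 per arm if split equally. **Assumed:** two-sided 5%, since no alpha is stated; arm SD equal to the pilot SD.

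**The plan's own figures.** Effect size = 3.764/2.135 = 1.763. A two-sample t-test at two-sided 5% has 90.6% power with 8 per group and 85.7% with 7, so the stated eight reproduces. (A one-sample test against zero would need only 6.) Enrolment: 8/0.45 = 17.8, rounded up to 18; 3 × 18 = 54.

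**How many usable sets to expect.** At the pilot rate, 54 × 5/11 = 24.5, about 8 per arm. The target of 45 would need 45/54 = 83% usable. The two statements conflict, so both sizes are carried through.

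**What an arm with an observed mean of exactly zero leaves open.** Half-width = t(0.975, n−1) × SD/√n, as a share of the pilot mean:

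- n = 8: 2.365 × 2.135/√8 = 1.785; 1.785/3.764 = 47%.
- n = 15: 2.145 × 2.135/√15 = 1.182; 1.182/3.764 = 31%.

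**What a result just short of significance leaves open.** The observed mean then lies one half-width from zero, so the far limit is two half-widths: 95% at n = 8 and 63% at n = 15.

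**Sensitivity at n = 8.** A 90% interval gives 38%. Pooling the SD over three arms (21 df) gives 42%. The 95% interval for an SD of 2.135 on 4 df is 1.28 to 6.14, which moves the 47% to between 28% and 136%.

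**Chance that a one-sample test within an arm misses a real residual.** Noncentral t, noncentrality = residual fraction × 1.763 × √n:

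| True residual | n = 8 | n = 15 |
|---|---|---|
| Half the pilot response | 43% | 11% |
| A quarter | 81% | 64% |

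**The between-arm contrast.** Half-width = t(0.975, 2n−2) × SD × √(2/n):

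- n = 8: 2.145 × 2.135 × √(2/8) = 2.290, or 61% of the pilot mean.
- n = 15: 2.048 × 2.135 × √(2/15) = 1.597, or 42%.

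If placebo showed the full pilot response and a remifentanil arm showed none, the lower limit for the reduction would be 100 − 61 = 39% or 100 − 42 = 58% of the pilot response. That establishes reduction, not elimination.

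**What a formal claim of elimination would need.** Two one-sided tests at 5% each with a true residual of zero: an illustrative margin of 50% of the pilot response has 47% power at n = 8 and needs about 16 usable per arm for 90%. A 25% margin needs about 58.

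**The case against.** The strongest reply is that the documents never say a non-significant arm will be read as elimination. They specify no within-arm test at all, and the stated eight fits a comparison between two groups. That is correct. A reader might infer that the plan equates failure to detect with elimination, but the text does not support this; the fault is an omitted rule. The miss rates describe a one-sample test chosen here for illustration, and they depend on supposed residuals of a half and a quarter. They do not predict how often the trial would be wrong.

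A reader might also infer that the outcome has no direction. It has one: 'reduced' refers to the size of the response, and the Figure 2 caption speaks of magnitude in the same sense. Only the hemoglobin series, the expected sign and the sidedness of any test are open.

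Nor should 47% be taken as a fixed property of the design. It needs eight usable sets, an observed mean of exactly zero and an SD from five subjects.

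Finally, section 2 places further clinical trials after this study, and section 8 says that its outcome will not affect clinical decisions, so no immediate harm to patient care follows.

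What survives is that the outcome offers a conclusion for which the plan has no definition, estimate or interval. Reading the design as a between-arm contrast does not rescue that conclusion, because its interval is wider than the single-arm one.

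**Conclusion.** The point holds as an omission with a measurable consequence. Under the pilot SD and a two-sided 95% interval, the most favourable flat result excludes only residuals above 47% of the pilot response at eight usable sets, or above 31% at 15. A borderline non-significant result excludes only those above 95% or 63%. The larger usable-data target shrinks the problem without removing it, and the pilot SD is too uncertain to rely on any of these as point figures. The 'reduced' half of the outcome is not undermined, but it needs a named series, region and sign before it can be tested. The change should be made before the data are analysed.

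**What to change.** In section 4.e and the Variables paragraph of the synopsis:

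- Drop 'eliminated' and keep 'reduced', defined as the difference from placebo in the response of one named hemoglobin series in one named region, with movement toward zero counted as reduction.
- In section 5.c, add that this difference will be reported for each remifentanil arm with a 95% confidence interval, together with the arm's residual response relative to placebo and its 95% interval. The latter is a ratio, so name the method (Fieller's, for example).
- State that a flat trace or a non-significant arm will not be reported as elimination.
- Reconcile the eight usable sets per group with the 45 useful sets overall, so that the expected precision can be stated.

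This needs no additional subjects or procedures. The cost is a more modest permitted claim, a little more analysis, and a commitment to one series and region in advance. If the investigators wish to keep elimination as a claim, they would instead have to justify a margin and size the arms for it.

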Statistical Issues: In our pilot study, we were able to collect useable data from five of the eleven subjects that were enrolled (45%). In the five subjects that produced usable results, the signal of interest had a mean value of -3.764×10^{-7} Moles with a standard deviation of 2.135×10^{-7} Moles. This results in a standardized effect size of 1.763, when using a zero mean for the null case. In order to achieve a 90% power level for this measure, the number of usable data sets is therefore eight. Considering our previous success rate of 45%, approximately 18 subjects will need to be enrolled into each group of the study for a total enrollment of 54 subjects. The data analysis will first be performed on a within-subject basis. Then, the original raw optical time series will be averaged across subjects (for corresponding optode placements only, standardized relative to the EEG 10-20 system).

1. Specific Aims /Objectives

The primary aim is to utilize near-infrared spectroscopy (NIRS) in patients under general anesthesia to measure hemodynamic activations in the bilateral somatosensory cortices and the prefrontal cortices in response to the noxious stimulation (pain) associated with catheter ablation of arrhythmias. Randomization of patients to placebo or one of two opioid doses should allow for discrimination between cortical activation and scalp sympathetic changes in response to pain.

Secondary aims are to utilize NIRS to measure hemodynamic activation in the supplemental motor area to actual or intended movement either spontaneously or in response to pain, and in the auditory cortices in response to auditory stimuli.

This study is part of an ongoing project to determine the value of NIRS as a tool for measurement of pain during general anesthesia and to monitor depth of anesthesia in order to prevent awareness.

2. Background and Significance

Anesthesia is a state of drug-induced unconsciousness with suppression of sensory perception, differing from normal sleep by the intensity of stimulus required to awaken the brain to conscious perception. Anesthesia can be defined by hypnotic (unconsciousness) and analgesic (pain relief) components, so that clinical anesthesia involves the administration of hypnotic and analgesic agents with the anesthesiologist observing the clinical response to noxious stimuli and adjusting the dosage to achieve an adequate depth of anesthesia.

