Prior to the induction of general anesthesia, we will perform the following to test optode placement and signal quality:

1. Resting state data will be collected for about 200 seconds while the patient is quietly lying still. This baseline data will be used to compare changes observed during the catheterization procedure.
2. Auditory Stimuli: Headphones will be placed on the subject's head and an audio recording will be presented to the subjects. This data will be used as baseline consciousness data, as well as to familiarize the subject with the study procedures. In order to activate the Supplemental Motor Area (SMA), which should be quiet unless patients move, we will adapt a previously employed method for evaluating subjects in the vegetative state (Owen, Coleman et al. 2006). The auditory stimulus will be presented for 5 seconds, with a varied inter-stimulus interval. The prompt will request that the subject imagine squeezing a tennis ball in their right hand in a clasping motion, without actually performing the action. During this we expect SMA activity to occur if the subject is consciously aware.
3. . The subject will be asked to perform a brief finger tapping exercise, tapping the fingers of the left hand against the thumb for 5 seconds, with 15 seconds between, for 5 cycles. This will only be conducted if time permits.
4. . Brush stimuli will be applied to the dorsum of the left hand in a similar manner. This will only be conducted if time permits.

4.

A BIS (Bispectral Index) monitor will be used in all study patients in order to control the depth of anesthesia. A BIS sensor will be placed on the forehead and a BIS value between 40 and 60 will be targeted. A BIS <60 is advocated to prevent awareness during general anesthesia (Avidan, Zhang et al. 2008). This will also allow for reduced variability in the depth of anesthesia between the subjects during the ablations.

During the Procedure:

The audio stimuli will be presented to the subject every half hour throughout the procedure. Near-infrared signals are measured and recorded by the NIRS device (TechEn CW 7) throughout the procedure and will not influence the procedure.

The anesthetic technique will be standardized for all study subjects, and will comprise the following:

Premedication: Midazolam 0.05 mg/kg IV up to a maximum of 2 mg
Induction: Fentanyl 1.5 mcg/kg IV up to a maximum of 3 mcg/kg. No fentanyl after induction.
Propofol – standard dosage titrated to effect

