optical contact with the scalp. The optodes are contained within a cap which will be placed on the patient's head in the catheterization laboratory. The light passes harmlessly through the subject's scalp onto the brain surface and returns, with some attenuation, to the detector optodes. The returning light yields information about blood-oxygenation levels in that region of the brain. The probe cap is not constricting and any discomfort will be minimized by surrounding the optodes with foam tape and using soft cloth straps against the head and face. After initial positioning, the probe may need to be shifted slightly until adequate signal is obtained through all detector fibers. In some cases, hair will be parted in order to achieve better optical contact. There will be no shaving of hair.

Prior to induction of general anesthesia, baseline activation signals of the somatosensory cortices and prefrontal cortices will be obtained in response to finger-tapping and brush stimuli applied to the dorsum of the hand as described above. This will provide baseline information to compare to the signals obtained during the procedure from surgically-induced pain.

In order to activate the Supplemental Motor Area, which should be quiet unless patients move, headphones will be placed on the subjects and an audio recording will be presented to subjects. The prompt will request that the subject imagine squeezing a tennis ball in their right hand, in a clasping motion, without actually performing the action. During this we expect SMA activity to occur if the subject is consciously aware based on similar results from prior studies. The audio stimuli will be presented to the subject every half hour throughout the procedure.

2. Patients will be randomized into one of three groups to receive an infusion which will be started after induction of general anesthesia while the patient is being prepped.

Group 1: 0.9% NaCl infusion

Group 2: Remifentanil 0.25 mcg/kg/min infusion

Group 3: Remifentanil 0.5 mcg/kg/min infusion

The infusions will be prepared by the hospital pharmacy. Investigators performing analysis of the NIRS signals will be blinded to the infusion the patient received. Infusions will be stopped after the cardiologist informs the anesthesiologist that no further ablations will be performed.

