The NIRS instrument will acquire raw data from each detector at ~40 kHz. The individual signals will then be bandpass filtered. Next, the time series pairs from each detector will be converted from wavelength (absorption) to relative concentrations (of oxy-/deoxy-hemoglobin). This will be done with the modified Beer-Lambert Law and the absorption coefficients of oxy- and deoxy-hemoglobin (HbO and Hb, respectively). (The near-IR wavelengths are chosen because oxy-/deoxy-Hb are the predominant absorbers in the tissue at these wavelengths.) The result will be an oxy-Hb and deoxy-Hb time series associated with each source-detector pair.

For each stimulation run, each smoothed oxy-/deoxy-hemoglobin time series will be examined for periodic amplitude fluctuations. Expected fluctuations include heart rate (~1-3 Hz), breathing and/or “v-waves” (~0.1Hz), as well as any fluctuations induced by the experimental paradigm. If the former sources of noise are substantial, an attempt will be made to filter out these fluctuations (in Fourier space). Any analysis of filtered data will be compared to an analysis of the corresponding non-filtered data. The oxy-hemoglobin portion of the experimentally-induced changes are expected to be 4-9 sec out of phase with the paradigm onsets and offsets (as seen in fMRI work as well as in prior optical recordings).

The data analysis will first be performed on a within-subject basis. Then, the original raw optical time series will be averaged across subjects (for corresponding optode placements only, standardized relative to the EEG 10-20 system).

The biological basis for the signals measured by the optical technique is the same as the basis for fMRI and PET scanning. The regions to be sampled in these pilot studies will be several times larger than single voxels in fMRI scanning. Furthermore, experiments with similar optical instruments indicate that these instruments are at least as sensitive as fMRI. With larger sampling regions (up to a factor of 5 or more), and assuming only comparable sensitivity, the optical imaging should require no more subjects than an fMRI study, and perhaps fewer. Furthermore, optical recording can provide 10-100 times the temporal resolution of fMRI. So, since an optical time series would seem to be at least as good as that coming from an individual voxel (or small collections of voxels) from fMRI data, similar group sizes should be adequate for optical experiments (Boas, Dale et al. 2004).

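### Spontaneous SMA activation is part of the secondary outcome, but the plan records no movement event to tie it to and gives no under-anesthesia null to judge it against

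*Combined protocol and SAP*

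**What the plan says.** Section 4.e gives one secondary outcome: the use of NIRS to measure SMA activation to "actual or intended movement either spontaneously, in response to pain, and/or in response to auditory stimuli". The opening summary lists the same three triggers. Neither place orders them, gives a success rule or labels any of them exploratory. Section 1 states the aim differently: "measure hemodynamic activation in the supplemental motor area to actual or intended movement either spontaneously or in response to pain, and in the auditory cortices". There, the reaction to sound is placed outside the SMA.

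On timing, section 4.f has "Audio stimuli (5 seconds each) presented to the patient every half an hour", and staff "will document time and duration of ablations, times of catheter insertion and removal". Movement is not on that list, nor is it named among the data taken from the electronic anesthesia record. Recording is continuous: "Near-infrared signals are measured and recorded by the NIRS device (TechEn CW 7) throughout the procedure" (section 4.a). Section 4.f adds: "Average duration of an electrophysiologic study with catheter ablation of arrhythmias is 3 to 4 hours".

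On analysis, section 5.c says "The data analysis will first be performed on a within-subject basis", followed by averaging of the raw series across subjects. It works by stimulation run, with latency counted from the paradigm's onsets and offsets. It gives no SMA channel set, window, threshold, test, alpha or multiplicity rule, and says nothing about stimulus-free recording. The resting comparator in section 4.a is about 200 s, taken before induction.

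**The concern.** Two of the three triggers have known times. The third does not. Without an independent movement record, the only route to spontaneous SMA activation is to look along the recording for an SMA rise and infer a movement or an intention from it. That reasoning is circular, and the plan sets no limit on the number of looks.

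An SMA rise carries weight in this project. Sections 4.a and 4.d say of the auditory prompt: "During this we expect SMA activity to occur if the subject is consciously aware". The wider aim is to monitor anesthetic depth so as to prevent awareness. Fluctuation reported as intended movement under anesthesia would be a consequential claim, and the plan as written offers no means of separating it from noise.

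**Working it through.** **The plan's own figure.** The only sample-size calculation is in section 5.d: effect size 3.764/2.135 = 1.763, 8 usable data sets, 18 enrolled per group, 54 in total. Alpha is not stated. With an assumed two-sided 5% two-sample t-test, 8 per group gives power 0.906 (7 gives 0.857); 8/0.45 = 17.8, rounded up to 18; and 3 × 18 = 54. The figure reproduces, but it concerns the pilot signal of interest. Nothing is calculated for the SMA outcome.

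**Is there an event to lock to?**

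- Auditory: yes. One prompt every half hour over 3 to 4 h gives about 6 to 8 per subject.
- Pain: yes. Ablation times and durations are logged.
- Spontaneous, actual movement: an observed movement could serve, but no log of movement is planned.
- Spontaneous, intended movement: no outward sign, hence no marker other than the NIRS signal itself.

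**Is there a null?** The resting segment of about 200 s is taken after light sedation but before induction. It does not represent SMA fluctuation over hours of general anesthesia. The other pre-induction recordings (prompt, finger tapping, brush) are responses to stimuli, so they are not a null either. Section 4.d expects the SMA to be quiet in the absence of movement, but this is not turned into a criterion. Section 5.c itself expects physiological fluctuation, including some near 0.1 Hz, and promises only an attempt to filter it if substantial.

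**How far could an unlocked search mislead?** This is illustration only. Assumptions: one SMA channel, and one independent look every 300 s to allow for strong autocorrelation. The number of looks is m = hours × 3600/300, which is 36 at 3 h and 48 at 4 h. The chance of at least one false activation per subject is 1 − (1 − a)^m, where a is the level per look:

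| a per look | m = 36 | m = 48 |
|---|---|---|
| 5% | 0.842 | 0.915 |
| 1% | 0.304 | 0.383 |
| 0.1% | 0.035 | 0.047 |

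Shorter spacing raises these values. With independent 20 s windows (m = 540 and 720) the chance is above 0.999 at 5% and 0.42 to 0.51 at 0.1%. If only rises count, at 2.5% per look, 36 to 48 looks give 60% to 70%. Holding 5% per subject by Bonferroni needs 0.05/36 = 0.0014 to 0.05/48 = 0.0010 per look. More channels or both chromophores would raise the rates; stronger autocorrelation would lower them.

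**Contrast with an event-locked test.** Testing each of 6 to 8 prompts singly at 5% gives 1 − 0.95^6 = 0.26 to 1 − 0.95^8 = 0.34. One pre-specified test on the average over prompts holds 5%. The exposure comes from the missing event and the missing rule, not from the SMA measurement as such.

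**The case against.** The strongest reply is that no search is planned. The outcome is worded as use of NIRS to measure, with no success rule and no rule for calling a subject positive, so nothing is formally met and no stated error rate is breached. Grammatically, the word spontaneous describes the movement, so an observed movement could be the event. Section 5.c is event-locked in frame, and its second step averages across subjects, which would attenuate unlocked noise. Section 5.c also speaks of pilot studies, and section 8 says that the outcome will not affect clinical decisions.

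Most of this stands, and it rules out several stronger readings that a reader might infer:

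- **That chance alone can satisfy the outcome, or that the whole recording will be scanned.** No success rule exists, and no section proposes such a scan.
- **That nearly every subject would show a false activation.** That needs something like 5% per look. No level is stated, and the chance falls below 5% at 0.1% per look with the same 36 to 48 looks.
- **That spontaneous SMA activity would be read as awareness.** Sections 4.a and 4.d make that link only for activity during the prompt.
- **That false positives can be set against the awareness incidences in section 2 (0.1% to 0.8%).** Those are rates of intraoperative awareness, which the section itself regards as underreported. They are not rates of SMA response.

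The reply does not supply a movement record, a marker for intended movement, a treatment of stimulus-free recording, or a null recorded under anesthesia.

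**Conclusion.** The concern holds in a limited form. One of the three triggers in the secondary outcome cannot be assessed as planned: spontaneous intended movement has no event independent of the signal, and spontaneous actual movement has none that the plan records. The analysis section is silent on the part of the recording where such activation would have to be found, and the pre-induction resting segment is not a suitable null for it.

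The size cannot be derived from the documents. The illustrative per-subject chance of at least one false activation runs from 3.5%–4.7% to 84%–91% for 36 to 48 looks, depending on a level per look that the plan leaves open. That spread is itself the finding: the reader of a positive result could not tell where in the range it lies. The figures rest on independent looks, a single channel and the average procedure length. The primary outcome is not affected.

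**What to change.** **Section 4.e.** List two separate secondary outcomes: the prompt-locked SMA response and the ablation-locked SMA response. Gate neither on the other. The prompt response is expected only in a conscious subject and a BIS of 40 to 60 is targeted, so testing the ablation response only after a positive prompt response would probably lose the pain result. Use Holm across the two; at an overall 5%, which the plan would need to state, the smaller p-value is compared with 2.5% and, if that passes, the larger with 5%. Label spontaneous SMA activity exploratory and report it descriptively.

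**Section 5.c.** Name the SMA channels, the chromophore, the response window and the statistic (for example, the mean over all events of that type in the subject). Compare it with the same statistic at randomly drawn sham times in the same under-anesthesia recording, away from prompts and ablations. Apply multiplicity control across subjects before any individual is called positive.

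**Section 1 against section 4.e and the opening summary.** Reconcile whether the auditory response is assessed in the auditory cortices, the SMA or both. If both, count both in the adjustment.

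**Cost.** Wording changes and a small amount of resampling on data already recorded; no new patients, staff or procedures. The trial gives up any claim to have detected spontaneous intended movement.
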